### (1) Purpose of Surveillance Study

To confirm the effectiveness and safety of the Conformable GORE® TAG® Thoracic Endoprosthesis (hereinafter referred to as "Device") in post-marketing utilization for the new indications of acute complicated Stanford Type B aortic dissection and traumatic thoracic aortic transection.

### (2) Number of subjects to be surveyed and Rationale for setting the number

Number of subjects to be surveyed: 43 subjects with acute complicated Stanford Type B aortic dissection.

Rationale for Setting:

### (3) Target Patients for Surveillance Study

Among patients with acute complicated Stanford Type B aortic dissection of descending thoracic aorta who meet all of the following anatomic requirements, those who have not responded to medical therapy.

- Have adequate iliac and femoral artery access route
- Aortic inner diameter at the leading end of the proximal landing zone is within the range of 16-42mm.
- ≥20mm landing zone is on proximal side of primary entry tear and there is no dissection at the leading end of the landing zone.

### (5) Method of Surveillance Study

- 1) The request for cooperation in this surveillance study should be notified to the sites in advance, and the sites should contact our company as soon as the eligible subjects are identified. A written contract for the survey shall be concluded between the sites for the survey, the company, and the company's subcontractor.
- 2) The sites complete and submit the results of surveillance study questionnaire within 1 month and 1 year after implantation of the Device, and annually thereafter until the completion of the fifth year of the survey.
- 3) In case device failure is recognized, physician in charge or person in charge at our company's subcontractor will immediately contact the person in charge of the survey at our company, and in-house safety management department will take necessary action.
- 4) An annual report of the survey is prepared every year after the start of the survey, and submitted to the Pharmaceuticals and Medical Devices Agency after internal evaluation and approval by post-marketing surveillance department and safety management department.

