**(7) Items to be surveyed, etc.**

- 1) Items to be surveyed
  - ① Information on Subject and Procedure
    - Background of patient, preoperative patient information, etc.
    - Information on the use of the Device
    - Use and place of ballooning
    - Additional procedure at the time of treatment and detailed information
    - Hospitalization period
  - ② Safety endpoints
    - Death
    - Serious adverse events (including stroke, respiratory failure, cardiac infarction, renal failure, paraplegia/paraparesis, and bowel ischemia)
  - ③ Effectiveness endpoints
    - Primary Entry Tear Exclusion
    - Aortic rupture
    - Primary Events related to the devices
    - Incidence rate of secondary interventional treatment (including additional implantation of the Device and conversion to surgical operation), description of the procedure, and reasons for intervention
    - Change in true and false lumen diameters
- 2) Priority Survey Items, Rationale for Setting and Specific Survey Methods  
Priority Survey item: All-cause mortality for 30 days  
Rationale for Setting: [REDACTED]

[REDACTED]

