**(8) Items and Methods for Analysis**

- 1) All-cause Mortality Rate  
Of the number of valid subjects in each evaluation period, the percentage of subjects with reported deaths is shown and is used as a characteristic evaluation.
- 2) Serious Adverse Events  
Of the number of valid subjects in each evaluation, the percentage of subjects with reported adverse events including stroke, respiratory failure, cardiac infarction, renal failure, paraplegia/paraparesis, and bowel ischemia is shown and is used as a characteristic evaluation. Causal relationships※1 are investigated for each event.

Causal relationships※1

For each report of an adverse event, the physician in charge evaluates the primary relationship to the Device or procedure as follows.

- Not related to the Device or procedure -In case the cause or primary cause of an adverse event is due to a cause not related to the Device or procedure

- Related to the Device - The cause or primary cause of an adverse event is due to a function or characteristic of the Device
- Related to TEVAR - In case the cause or primary cause of an adverse event is due to TEVAR procedure (not due to the Device)
- Related to concomitant procedure - In case the cause or primary cause of an adverse event is due to concomitant procedure (not related to the Device or TEVAR)
- Unknown relation -Causal relationship with an adverse event cannot be determined

3) Primary Entry Tear Exclusion

Of subjects confirmed to have primary entry tear in each evaluation period, the percentage of those with primary entry tear is calculated. Confirm that primary entry tear exclusion is not significantly lower than that in TAG 08-01 study.

4) Aortic Rupture

Of the number of valid subjects in each evaluation period, the percentage of subjects with aortic rupture is shown and is used as a characteristic evaluation.

5) Primary events related to the Device

Of the number of valid subjects in each evaluation period, the percentage of subjects with a primary events related to the device※2 is shown and is used as a characteristic evaluation.

Primary events related to the device※2

Events reported as endoleak, access and deployment failure, luminal obstruction (including device compression and thrombus), stent graft structural failure, extrusion/erosion, stent graft migration, migration between components, and wire fracture, as well as selected as primary in severity.

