2.2 Method of Surveillance Study

The request for cooperation in this surveillance study should be notified to the sites in advance, and the sites should contact our company as soon as the eligible subjects are identified. A written contract for the survey shall be concluded between the sites for the survey, the company, and the company's subcontractor.

In case device failure is recognized, physician in charge or person in charge at our company's subcontractor will immediately contact the person in charge of the survey at our company, and in-house safety management department will take necessary action.

The sites complete and submit the results of surveillance study questionnaire within 1 month and 1 year after implantation of the Device, and annually thereafter until the completion of the fifth year of the survey.

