2.3.1 Safety Data

All-Cause Mortality (Dissection and Trauma)

All-cause mortality through 30 days post-treatment will be evaluated. For the dissection cohort, this result will be compared descriptively with the performance goal of 0.25 from the TAG 08-01 study. Additionally, Kaplan-Meier plots of all-cause mortality will be generated.

Serious Adverse Events (Dissection and Trauma)

The proportion of subjects reporting serious adverse events (including stroke, respiratory failure, myocardial Infarction, renal failure, paralysis/paraparesis and bowel ischemia) among the eligible subjects in each follow-up period shall be provided.

CONFIDENTIAL INFORMATION

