2.3.2 Efficacy Data

Primary Entry Tear Exclusion (Dissection)

The proportion of subjects reporting exclusion of the primary entry tear shall be evaluated among the eligible dissection subjects in each follow-up period. The result in the one month study window will be compared descriptively with the primary efficacy endpoint result from the TAG 08-01 study.

Aortic Rupture (Dissection and Trauma)

The proportion of subjects reporting aortic rupture among the eligible subjects in each follow-up period shall be provided.

Major Device Events (Dissection and Trauma)

The proportion of subjects reporting major device events among the eligible subjects in each follow-up period shall be provided. Major device events include endoleak, access and deployment failure, lumen obstruction (including device compression and thrombus), device integrity events, extrusion/erosion, device migration, intercomponent migration and wire fracture with severity from major A to major D selected.

Secondary Interventions (Dissection and Trauma)

The proportion of subjects reporting secondary interventions among the eligible subjects in each follow-up period shall be provided with the treatment and reason of the intervention.

True and False Lumen Diameter Changes (Dissection)

Changes in true lumen and false lumen measurements in both the treated segment and distal to the treated segment among the eligible dissection subjects in each follow-up period shall be provided. Changes of ≥ 5 mm will be considered an increase, changes of ≤ -5 mm will be considered a decrease, and changes between -5 mm and 5 mm will be considered stable.

Lesion Diameter Changes (Trauma)

Changes in lesion diameter among the eligible trauma subjects in each follow-up period shall be provided. Changes of ≥ 5 mm will be considered an increase, changes of ≤ -5 mm will be considered a decrease, and changes between -5 mm and 5 mm will be considered stable.

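### Does a first form due within 1 month of implantation miss the 1-month visit and day-30 survival?

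*Protocol*

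**What the plan says.** Protocol (5) 2) has the sites "complete and submit the results of surveillance study questionnaire within 1 month and 1 year after implantation of the Device, and annually thereafter", up to the end of year five. SAP 2.2 uses the same words ("questionnaire within 1 month and 1 year after implantation of the Device"). Neither document defines a month in days or states which visit each form covers.

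Protocol (8) 8) and SAP Table 1 agree on the visits. The 1-month visit is desirable on days 23-44 and analysed over days 15-59. The 6-month visit is desirable on days 150-210 and analysed over days 60-242. The 12-month visit is desirable on days 275-455 and analysed over days 243-546.

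Two dissection results depend on this early period:

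- **30-day mortality.** Protocol (7) 2) states "Priority Survey item: All-cause mortality for 30 days". The heading above it reads "Priority Survey Items, Rationale for Setting and Specific Survey Methods", and the text that follows is redacted. SAP 2.3.1 says "All-cause mortality through 30 days post-treatment will be evaluated" and adds "For the dissection cohort, this result will be compared descriptively with the performance goal of 0.25 from the TAG 08-01 study". It also plans Kaplan-Meier plots of all-cause mortality. Protocol (8) 1) reports deaths by evaluation period: "Of the number of valid subjects in each evaluation period, the percentage of subjects with reported deaths is shown".
- **Entry tear exclusion.** SAP 2.3.2 says "The result in the one month study window will be compared descriptively with the primary efficacy endpoint result from the TAG 08-01 study".

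**The concern.** If the sentence sets a hard deadline, a site can keep to the visit schedule, submit its first form on time, and still leave the 1-month visit off that form, because the visit may properly take place up to day 44. A form sent before day 30 also cannot establish that the subject survived 30 days.

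The results exposed are the two that the SAP sets against TAG 08-01: 30-day mortality and one-month tear exclusion. The next scheduled form is at 1 year. Meanwhile annual reports go to the agency (Protocol (5) 4)) and analyses run throughout enrolment and follow-up (SAP 4.2). An interim mortality figure could then rest on subjects whose day-30 status is not yet known, and the visible text does not say how to count them. With 43 dissection subjects, a few unknowns would be visible in the percentage.

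**Working it through.** No published figure has to be reproduced; the check is day counting.

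**Inputs.** The windows come from Protocol (8) 8) and SAP Table 1, and the target of 43 from Protocol (2). The length of a month is an assumption: day 30, varied from day 28 to day 31.

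**1. Literal deadline at 1 month.** The desirable window has 44 − 23 + 1 = 22 days and the analysis window 59 − 15 + 1 = 45 days. With the deadline on day d, the shares falling after it are (44 − d)/22 and (59 − d)/45.

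| d | Desirable days after d | Analysis days after d |
|---|---|---|
| 28 | 16/22 = 73% | 31/45 = 69% |
| 30 | 14/22 = 64% | 29/45 = 64% |
| 31 | 13/22 = 59% | 28/45 = 62% |

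The two requirements can still be met together: with d = 30, a visit and form on days 23-30 (22 − 14 = 8 desirable days) satisfy both.

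**2. The same reading at 1 year.** The desirable window has 455 − 275 + 1 = 181 days with midpoint (275 + 455)/2 = 365. Days after 365: 455 − 365 = 90, and 90/181 = 50%. The analysis window has 546 − 243 + 1 = 304 days; 546 − 365 = 181, and 181/304 = 60%. The later annual desirable windows are built in the same way, with midpoints at days 730, 1095, 1460 and 1825, which are 2, 3, 4 and 5 times 365. Visits are therefore meant to fall on either side of each anniversary. A sentence that cut these windows in half would contradict the whole schedule, which points to loose wording for forms tied to the 1-month, 1-year and annual visits.

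**3. The 6-month visit.** It has a row in both tables, but the form schedule goes from 1 month to 1 year. If 6-month results are to be reported, a later form has to carry them. The same route can carry a 1-month visit held after the first form was sent.

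**4. Day 30 when the form is completed at the visit.** Desirable days before day 30 are days 23-29: 7/22 = 32%. Analysis days before day 30 are days 15-29: 15/45 = 33%. A subject seen on day 25 and contacted again at any time after day 30 has known day-30 status. Only a subject with no contact after a visit on those days stays unknown.

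**5. Delay and size.** If nothing arrives before the 1-year form, the wait is 365 − 30 = 335 days, or 455 − 30 = 425 days if that form follows a visit at the end of its desirable window. One subject is 1/43 = 2.3 percentage points, so u subjects of unknown status leave a crude mortality range u × 2.3 points wide. The documents give no basis for estimating u.

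**The case for a change.** The case for a change is that the conflict lies between sentences printed in full, in both documents, and that it exists for any length of month. The kinder reading does not answer everything: a visit on days 23-29 is on schedule, yet it cannot show survival to day 30, and day 30 is not the edge of any evaluation period. Protocol (8) 1) uses a denominator of valid subjects without defining it. The immediate contact in Protocol (5) 3) covers device failure only, and SAP 4.5 shows no time limit for adverse event reports. A subject lost before the 1-year form could stay unknown for the priority item. A wording change would cost little and add no visits.

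The mismatch in wording stands, and so do the day counts. The consequence drawn from them is weaker. Completing a form at the visit is the natural reading once the 12-month row is considered. A subject lost after an early visit is an ordinary missing-data matter that arises with any window opening before day 30; moving a form deadline would not remove it. Kaplan-Meier plots need death and last-contact dates, and the estimate at day 30 handles follow-up that ends earlier by censoring. A day-30 rule may also exist in the redacted text under the priority item, so its absence cannot be asserted.

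**Conclusion.** No change to the plan is needed. The deadline wording is most likely a clerical looseness, and the missing rule for unknown day-30 status is a gap that analysts would fill sensibly: count day-30 survivors from status known at day 30 or later, or read the Kaplan-Meier estimate at day 30, and state how many are unknown.

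The likely effect is at most late 1-month or day-30 data in an interim report, not a wrong final result. The SAP treats both comparisons with TAG 08-01 as descriptive and plans no formal test (2.4), so no error rate is at stake. Protocol (8) 3) words the tear-exclusion comparison more strongly, but form timing does not bear on that difference.

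This rests on three assumptions: sites complete forms at or after the visits they report; later forms carry earlier visits and dates of death; and few subjects are lost between an early 1-month visit and any later contact. The 64% and 32% figures are shares of calendar days, not of subjects, and should not be read as expected losses. Stating which visit each form covers would be a harmless editorial clarification, but the analysis does not depend on it.

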### (6) Scheduled Period of Surveillance Study

Enrollment period: Enrollment continues until 43 subjects with complicated acute Stanford Type B aortic dissection treated with the Device has been enrolled. The enrollment period is expected to be [REDACTED].

Observation period: 5 years after the implantation of the Device

Rationale for Setting:

[REDACTED]

[REDACTED]

[REDACTED]

[REDACTED]

**(7) Items to be surveyed, etc.**

- 1) Items to be surveyed
  - ① Information on Subject and Procedure
    - Background of patient, preoperative patient information, etc.
    - Information on the use of the Device
    - Use and place of ballooning
    - Additional procedure at the time of treatment and detailed information
    - Hospitalization period
  - ② Safety endpoints
    - Death
    - Serious adverse events (including stroke, respiratory failure, cardiac infarction, renal failure, paraplegia/paraparesis, and bowel ischemia)
  - ③ Effectiveness endpoints
    - Primary Entry Tear Exclusion
    - Aortic rupture
    - Primary Events related to the devices
    - Incidence rate of secondary interventional treatment (including additional implantation of the Device and conversion to surgical operation), description of the procedure, and reasons for intervention
    - Change in true and false lumen diameters
- 2) Priority Survey Items, Rationale for Setting and Specific Survey Methods  
Priority Survey item: All-cause mortality for 30 days  
Rationale for Setting: [REDACTED]

[REDACTED]

**(8) Items and Methods for Analysis**

- 1) All-cause Mortality Rate  
Of the number of valid subjects in each evaluation period, the percentage of subjects with reported deaths is shown and is used as a characteristic evaluation.
- 2) Serious Adverse Events  
Of the number of valid subjects in each evaluation, the percentage of subjects with reported adverse events including stroke, respiratory failure, cardiac infarction, renal failure, paraplegia/paraparesis, and bowel ischemia is shown and is used as a characteristic evaluation. Causal relationships※1 are investigated for each event.

Causal relationships※1

For each report of an adverse event, the physician in charge evaluates the primary relationship to the Device or procedure as follows.

- Not related to the Device or procedure -In case the cause or primary cause of an adverse event is due to a cause not related to the Device or procedure

- Related to the Device - The cause or primary cause of an adverse event is due to a function or characteristic of the Device
- Related to TEVAR - In case the cause or primary cause of an adverse event is due to TEVAR procedure (not due to the Device)
- Related to concomitant procedure - In case the cause or primary cause of an adverse event is due to concomitant procedure (not related to the Device or TEVAR)
- Unknown relation -Causal relationship with an adverse event cannot be determined

3) Primary Entry Tear Exclusion

Of subjects confirmed to have primary entry tear in each evaluation period, the percentage of those with primary entry tear is calculated. Confirm that primary entry tear exclusion is not significantly lower than that in TAG 08-01 study.

4) Aortic Rupture

Of the number of valid subjects in each evaluation period, the percentage of subjects with aortic rupture is shown and is used as a characteristic evaluation.

5) Primary events related to the Device

Of the number of valid subjects in each evaluation period, the percentage of subjects with a primary events related to the device※2 is shown and is used as a characteristic evaluation.

Primary events related to the device※2

Events reported as endoleak, access and deployment failure, luminal obstruction (including device compression and thrombus), stent graft structural failure, extrusion/erosion, stent graft migration, migration between components, and wire fracture, as well as selected as primary in severity.

- Incidence rate of secondary interventional treatment (including additional implantation of the Device and conversion to surgical operation), description of the procedure, and reasons for intervention

Of the number of valid subjects in each evaluation period, the percentage of subjects with secondary interventional treatment and the details of the procedure/the reason for the intervention are shown and is used as a characteristic evaluation.

6) Change in true and false lumen diameters

Of the number of valid subjects in each evaluation period, subjects with the change in true and false lumen diameters of the treated site and the distal side of the treated site are shown and are used as a characteristic evaluation.

8) Evaluation period

Each evaluation period is as follow

Follow-up visit	Desirable period for visit (Number of days)	Evaluation period (Number of days)
Time of Operation	0	0
Time of Discharge	Before Discharge	None Specified
After Operation	1~14	1~14
1 Month	23~44	15~59
6 Months	150~210	60~242
12 Months	275~455	243~546
24 Months	640~820	547~911
36 Months	1005~1185	912~1275
48 Months	1370~1550	1276~1640
60 Months	1735~1915	1641~2006

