4.0 Statistical Analyses

4.1 Analysis Populations

All enrolled subjects will be included in reported data. Results will be reported separately for the dissection and trauma cohorts, unless specified otherwise.

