4.2 Timing of Analyses

Analysis of the study results will be ongoing throughout enrollment. Serial analyses of long-term results will occur during the follow-up period. No adjustment to overall alpha level will be made for this surveillance study.

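### Does the 30-day mortality figure set beside 0.25 count subjects not yet followed to day 30 as survivors?

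*Protocol*

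**What the plan says.** Protocol section (7) 2) names the priority item: "Priority Survey item: All-cause mortality for 30 days". Protocol section (8) 1) then describes the mortality analysis by period: "Of the number of valid subjects in each evaluation period, the percentage of subjects with reported deaths is shown". It does not define which subjects are valid. The early evaluation periods in section (8) 8) are day 0, days 1 to 14 and days 15 to 59, so none ends at day 30.

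SAP 2.3.1 evaluates all-cause mortality through 30 days after treatment. It continues: "For the dissection cohort, this result will be compared descriptively with the performance goal of 0.25 from the TAG 08-01 study". It adds Kaplan-Meier plots of all-cause mortality. It gives no denominator for the 30-day figure and no rule for subjects with shorter follow-up.

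Three other statements bear on the point:

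- SAP 4.1: "All enrolled subjects will be included in reported data".
- SAP 4.2: "Analysis of the study results will be ongoing throughout enrollment".
- Protocol section (5) 4): "An annual report of the survey is prepared every year after the start of the survey", after which it goes to the regulator.

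SAP 2.4 rules out formal hypothesis tests, and SAP 4.3 rules out inferential analyses.

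**The concern.** Two things look wrong at first.

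The protocol's analysis section never produces the priority item. A set of per-period percentages is not a 30-day rate, and the 1-month period mixes deaths before and after day 30.

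The SAP supplies the right quantity but no denominator. If all enrolled subjects form the denominator of an analysis run during enrolment, someone implanted ten days before the data cut adds one to the denominator and, being alive so far, nothing to the numerator. The proportion can then only equal or fall below the 30-day mortality eventually seen in the same subjects. The error is in the device's favour, on the one mortality result that has a numerical benchmark, in reports that may reach the regulator. Close to 0.25, the choice of denominator alone could decide on which side of the goal the figure falls.

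**Working it through.** **Inputs from the documents.** There are 43 dissection subjects (protocol section (2)), and the goal is 0.25 (SAP 2.3.1). The basis for 43 is redacted, so that number cannot be reproduced. At 43 subjects the goal corresponds to 43 × 0.25 = 10.75 deaths: 10 deaths fall below it and 11 above.

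**Assumed inputs.** The documents show no accrual rate, death count or number of subjects with unknown status. All such values below are illustrations.

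**Step 1: per-period rates against a 30-day rate.** Suppose that of 43 subjects 3 die on day 0, 1 on days 1–14, 1 on days 15–30 and 1 on days 31–59.

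- Per period: 3/43 = 7.0%, 1/40 = 2.5%, 2/39 = 5.1%.
- Through day 30: 5/43 = 11.6%.

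The two summaries differ, so the 30-day figure has to come from SAP 2.3.1, and that section does provide it.

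**Step 2: how many subjects could be pending.** With even enrolment, the share implanted in the last 30 days is 30/182.5 = 16.4% at 6 months, 30/365 = 8.2% at 1 year and 30/730 = 4.1% at 2 years. With 21 enrolled at 1 year, that is 21 × 30/365 = 1.7 subjects.

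**Step 3: an interim report near the goal.** Take 21 enrolled, 5 deaths, and 2 subjects alive but short of day 30.

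- All enrolled: 5/21 = 23.8%.
- Known status only: 5/19 = 26.3%.
- Kaplan-Meier at day 30, with deaths on days 1, 3, 6, 9 and 25 and censoring on days 8 and 20: 1 − (18/21)(16/17)(14/15) = 24.7%.

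The Kaplan-Meier figure always lies between the other two. It equals 23.8% if both subjects are censored after the last death and 26.3% if both are censored before the first. With the days assumed here it stays on the same side of 0.25 as the all-enrolled proportion.

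**Step 4: expected dilution.** If m of N subjects are pending and counted as alive, a true rate r is reported on average as r(N − m)/N. For r = 0.28, N = 20 and m = 3, this is 0.28 × 17/20 = 0.238. With m = 0 it is 0.28.

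**Step 5: the full cohort.** The table gives the smallest number u of subjects with unknown day-30 status for which a known-status denominator moves the figure above 0.25.

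| Deaths | All 43 | u | Known status |
|---|---|---|---|
| 10 | 10/43 = 23.3% | 4 | 10/39 = 25.6% |
| 9 | 9/43 = 20.9% | 8 | 9/35 = 25.7% |
| 8 | 8/43 = 18.6% | 12 | 8/31 = 25.8% |

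Four of 43 is 9.3%. Nothing in the documents points to losses of that size within 30 days. With u = 0, the simple proportion and the Kaplan-Meier estimate are the same number.

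**Step 6: scale.** For 10 deaths in 43, the exact 95% interval is 11.8% to 38.6%. The denominator effect in the first row, 25.6 − 23.3 = 2.3 percentage points, is small beside it.

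**Step 7: what the text commits to.** SAP 4.1 says who appears in the reports and then that the cohorts are reported separately; it does not say how an unobserved outcome is scored. SAP 4.2 says when analyses run, and protocol section (5) 4) says that a report is written. Neither says that the comparison with 0.25 is repeated each time. Counting pending subjects as survivors is one reading of these sections taken together, not a stated rule.

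**The case for a change.** The best case for a change is that this is the priority item, that the SAP limits other endpoints to eligible subjects in each follow-up period but puts no such limit on mortality, and that the only visible population statement is all enrolled subjects. One sentence naming the day-30 Kaplan-Meier estimate would settle the matter and needs no new data.

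The form schedule adds some weight: "The sites complete and submit the results of surveillance study questionnaire within 1 month and 1 year after implantation of the Device". The ideal 1-month visit window is days 23 to 44, so a form completed on days 23 to 29 meets both rules and leaves day-30 status open until a later contact.

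Part of this stands. The visible text is silent on the denominator and on incomplete follow-up, the protocol's own analysis section gives no 30-day rate, and an all-enrolled denominator would lower an interim figure. Step 4 shows that this can carry a rate across 0.25 early in enrolment.

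The rest is weaker. Silence is not a wrong rule, and the one method named for mortality that deals with incomplete follow-up is the right one. A status left open at day 25 is settled by the next form, because a subject alive at 1 year was alive at day 30. The documents do not show how often forms would come early. Redacted text may also hold the missing detail: protocol section (7) 2) after the priority item, SAP 4.3, and the SAP subsections whose headings are blank (5.1, 5.2 and 6.1 to 6.3), the last group under the list of planned tables.

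**Conclusion.** No change follows. The visible plan leaves the denominator of the 30-day figure unstated; it does not prescribe a wrong one. SAP 2.3.1 supplies the 30-day analysis that protocol section (8) 1) lacks, and an SAP that fills in a short protocol does not contradict it. A competent analyst would censor pending subjects, or report how many there are, with the Kaplan-Meier analysis already planned.

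The possible effect is confined to reports issued before day-30 status is complete. In the assumed report with 21 subjects it is at most 26.3 − 23.8 = 2.5 percentage points, and 0.9 points with the event days used. At the end of the study it is zero if every subject's day-30 status is known. With 43 subjects and 10 deaths, even a known-status denominator would need 4 unknown statuses to exceed 0.25. Away from the goal the reading does not change.

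The comparison is descriptive, so no error rate is at stake, and no visible decision rule depends on an interim figure. The conclusion assumes that day-30 vital status is eventually obtained for nearly all subjects and that the redacted text does not prescribe counting pending subjects as alive.

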4.5 Adverse Events

Adverse Events (AEs) will be recorded on the appropriate Case Report Form (CRF). The Investigator at each Site is ultimately responsible for reporting all AEs. The most appropriate AE code will be chosen from the AE list and will also have an accompanying description. Each AE will be assessed by the Investigator to determine if it is: serious/non-serious, major/minor, and related to the device/TEVAR procedure/concomitant procedure as described in the CRF.

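### A sudden death of undetermined cause does not reach the rupture count, and no visible analysis sorts deaths by relationship code or aortic cause

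*Protocol*

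**What the plan says.** **Death.** In Protocol section (8), item 1), the mortality analysis for each evaluation period is that "the percentage of subjects with reported deaths is shown and is used as a characteristic evaluation". SAP 2.3.1 evaluates all-cause mortality through 30 days and then says: "Additionally, Kaplan-Meier plots of all-cause mortality will be generated". These are the only visible analyses of death.

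**Rupture.** Protocol section (7) lists aortic rupture as an effectiveness endpoint. Section (8), item 4), says of it that "the percentage of subjects with aortic rupture is shown and is used as a characteristic evaluation". SAP 2.3.2 ties the numerator to reports: "The proportion of subjects reporting aortic rupture among the eligible subjects in each follow-up period shall be provided". Neither document defines rupture, and neither says how a sudden or unexplained death is to be treated.

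**Relationship.** Under serious adverse events, Protocol section (8), item 2), states: "For each report of an adverse event, the physician in charge evaluates the primary relationship to the Device or procedure as follows". The five categories are the Device, TEVAR, a concomitant procedure, none of these, and an unknown relation, the last for when "Causal relationship with an adverse event cannot be determined". SAP 4.5 has the investigator assess whether each event is "related to the device/TEVAR procedure/concomitant procedure as described in the CRF", without naming the unknown category.

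**The concern.** The study has one arm and follows subjects for 5 years. Over that time all-cause mortality mixes deaths from treatment failure with deaths from unrelated causes, and there is no comparator to separate them. Rupture is the listed endpoint that speaks most directly to fatal failure of the treated aorta, yet it depends on someone diagnosing and reporting it. A subject who dies suddenly outside hospital, with no imaging and no autopsy, is recorded as a death and not as a rupture.

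The resulting error has one direction. Any such death that was in fact a rupture is missing from the count, which makes the Device look better. With 43 dissection subjects, a few deaths could decide whether late rupture appears absent or material. The visible plan gives a reader of the report no way to see how many deaths are in doubt.

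**Working it through.** **Inputs**
- Dissection subjects: n = 43 (Protocol section (2)).
- Observation: 5 years (Protocol section (6)); questionnaires are annual after the first year (section (5)).
- Late evaluation windows, from the table in Protocol section (8) and SAP Table 1: 24 months is 911 − 547 + 1 = 365 days; 60 months is 2006 − 1641 + 1 = 366 days. A death can fall well away from any scheduled visit.
- Counts of ruptures and of unexplained deaths: not given. All counts below are assumptions.

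The plan states no rupture rate, so there is no figure of its own to reproduce. The reasoning behind n = 43 is not in the public text and is not at issue here.

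**Step 1: where an unexplained sudden death appears**

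| Output | Does it appear? |
|---|---|
| All-cause mortality (Protocol (8) item 1; SAP 2.3.1) | Yes |
| Rupture (Protocol (8) item 4; SAP 2.3.2) | Not unless the site reports it as rupture |
| Relationship code (Protocol (8) item 2; SAP 4.5) | Yes, if the fatal event is reported as an adverse event |
| Deaths tabulated by relationship or aortic cause | No such analysis is visible |

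The relationship code asks about the Device, TEVAR and concomitant procedures. A death from progression of the underlying dissection could properly be coded as unrelated, so the code alone does not identify aortic deaths.

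**Step 2: does the undefined denominator change the direction?**

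The terms for valid subjects (Protocol) and eligible subjects (SAP) are not defined. Let x be the reported ruptures and k the deaths that were undiagnosed ruptures. Had they been diagnosed, the rate would be (x + k)/n.
- If those subjects stay in the denominator, the reported rate is x/n, which is short by k/n.
- If they drop out, it is x/(n − k). The shortfall is (x + k)/n − x/(n − k) = k(n − k − x)/[n(n − k)], which is never negative.

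With x = 1 and k = 1, the two readings give 1/43 = 2.3% and 1/42 = 2.4%, against 2/43 = 4.7%. Undiagnosed ruptures lower the rate under either reading.

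**Step 3: scale**

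One death moves the rate by 1/43 = 2.3 percentage points if all 43 are evaluable, and by more in a window with fewer evaluable subjects. Exact Clopper-Pearson 95% limits are Beta(0.025; x, n − x + 1) and Beta(0.975; x + 1, n − x) quantiles. For x = 0 the upper limit is 1 − 0.025^(1/43) = 8.2%.

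| Possible ruptures (assumed) | Rate | 95% interval |
|---|---|---|
| 0/43 | 0% | 0 to 8.2% |
| 1/43 | 2.3% | 0.1 to 12.3% |
| 2/43 | 4.7% | 0.6 to 15.8% |
| 3/43 | 7.0% | 1.5 to 19.1% |

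If no rupture is reported, zero to three deaths of undetermined cause give an upper-bound rate between 0% and 7.0%.

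**The case against.** The strongest reply is that the plan already collects what is needed. A fatal event reported as an adverse event receives a relationship code, and the Protocol's code includes an unknown category. Placing that code under serious adverse events does not exclude fatal ones. The CRF is not public, the contents of SAP section 6 are not shown, and part of SAP 4.3 is redacted, so a cause-of-death field or a death listing may exist. Failure of the treated aorta is also followed to 60 months through device events, secondary interventions with reasons, and lumen diameters. The study is descriptive, with no tests (SAP 2.4), and its priority item is 30-day all-cause mortality, which this point leaves alone.

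Much of this stands, and it rules out three stronger readings that a reader might infer:
- *That 5-year mortality cannot be read at all for aortic or device failure.* The relationship code would allow device- or procedure-related deaths to be partly identified.
- *That an unexplained death is counted as free of rupture and then leaves later denominators.* The denominators are undefined, so either treatment is possible.
- *That the true rupture rate is some multiple of the reported one.* Any multiple depends on the counts chosen, and the documents supply none. Nor do they say how often fatal ruptures go undiagnosed, or how a physician would report a suspected rupture.

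What the reply does not meet is narrower. Collecting a code is not the same as analysing it: neither mortality analysis applies it to deaths, it has no aortic category, and no visible rule covers unexplained deaths in the rupture endpoint. The other measures also need a subject who is alive and imaged, or an event that is recognised.

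**Conclusion.** The point holds as a gap in the specified analyses and does not show bias in this study's results. On the visible text, death is summarised only as all-cause, rupture enters only when reported, and nothing shows how many deaths might have been ruptures. The reported rate is too low to the extent that undetermined deaths were ruptures, and this error favours the Device.

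The size is about 2.3 points per such death. That assumes all 43 dissection subjects are evaluable and that the rate is taken over the cohort; the plan reports by window, where the step can be larger. The number of such deaths is unknown and may be zero. For the trauma cohort no sample size is set, so no scale can be given. This is a cheap improvement worth making; it does not undermine the mortality results.

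**What to change.** 1. **SAP 2.3.1:** tabulate every death by the existing relationship code, including the unknown category, and by one added item for aortic cause (yes, no, undetermined). Show related and undetermined deaths in separate rows; pooling them would overstate related deaths.
2. **SAP 2.3.2:** beneath the reported-rupture rate, add a sensitivity line in which deaths of undetermined cause also count as possible ruptures. Keep those subjects in the denominator of the window in which they died, and label the line as an upper bound.
3. **Unchanged:** all-cause mortality, including the 30-day result and the Kaplan-Meier plots, and the reported-rupture rate.
4. **Optional:** a competing-risk curve. With 43 subjects it may rest on very few events, and the table carries the main information.

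The cost is one extra item on the death report, if the CRF does not already hold it, and two descriptive outputs. No committee, visit or change in sample size is needed. The drawback is that the sensitivity figure will be equal to or less favourable than the reported one, and it will overcount where an undetermined death was not a rupture.
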